5.4.4. Secondary generalized seizures

5.4.4.1. Definition

Provided a large enough number of events are observed, separate analyses for focal to bilateral tonic-clonic seizures will be performed; namely, the same analysis as that of the primary endpoint and the analysis of the percent reduction.

There may be a number of participants with no focal to bilateral tonic-clonic seizures reported in the baseline period but reported some during the double-blind period. This would have an impact on the aforementioned analyses by reducing the analysis sample or resulting in undefined outcome for these participants. If this is the case, the time-to-event analysis and percent reduction analyses will not be undertaken and instead the response ratio will be calculated and analyzed. The response ratio will range from -1 to 1 and is defined as (T - B)/(T + B), where T is the double-blind monthly seizure count and B is the baseline monthly seizure count, where a negative ratio indicates improvement.

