#### Secondary generalized seizures

Separate analyses (including time to baseline count and % reduction of counts) for focal to bilateral tonic-clonic seizures will be performed if a large enough number of events is observed.

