5.4.4.2. Analysis Methods

For each cohort, the time to baseline seizure count will be analyzed for focal to bilateral tonicclonic seizures in the same way as described in Section 5.3.3 for the primary efficacy endpoint. Kaplan-Meier analyses will be presented for the time to reaching baseline monthly seizure count (with 95% CI) for each group (JNJ-813 or Placebo) pooled over CCI , and also treatment group by for all focal to bilateral tonic-clonic seizures. Descriptive summaries of the Kaplan-Meier estimates will be presented by treatment group (JNJ-813 or Placebo) pooled over and also treatment group by , which will include the median with 95% CI and quartiles. The hazard ratio and its 95% CI will be estimated using a Cox proportional hazard regression model, including treatment and baseline CCI . Primary endpoint data from participants on placebo in subsequent cohorts will be combined with those from the previous cohort(s) if the Kaplan-Meier curves of the participants treated with placebo are comparable between cohorts. Where placebo groups are comparable, Kaplan-Meier curves for each cohort will be presented together to demonstrate comparability prior to combining the placebo groups.

In addition, the percent reduction in the double-blind monthly seizure count will be analyzed as described in Section 5.4.1.2 for focal to bilateral tonic-clonic seizures by treatment group and stratum.

Descriptive statistics (N, mean, SD, median, 25th percentile and 75th percentile) will be summarized for each cohort by treatment group (JNJ-813 or Placebo) pooled over colors,

and also treatment group by CCI) where the response ratio approach is utilized.

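### SAP 5.4.4 lets an unquantified number of new-onset cases replace both tonic-clonic analyses with a ratio that is undefined for participants with no such seizures and fixed at its worst value for new-onset cases

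*SAP*

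**What the plan says.** Protocol 9.2.2 names two analyses for these seizures, subject to enough events: "Separate analyses (including time to baseline count and % reduction of counts) for focal to bilateral tonic-clonic seizures will be performed". It gives no fallback.

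SAP 5.4.4.1 repeats the condition ("Provided a large enough number of events are observed") without a number and plans the same two analyses. It then notes that there "may be a number of participants with no focal to bilateral tonic-clonic seizures reported in the baseline period but reported some" in the double-blind period, which would shrink the sample or leave the outcome undefined. The consequence is: "If this is the case, the time-to-event analysis and percent reduction analyses will not be undertaken and instead the response ratio will be calculated".

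The ratio "is defined as (T - B)/(T + B), where T is the double-blind monthly seizure count" and B is the baseline one. Its stated range is -1 to 1, and negative values mean improvement.

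SAP 5.4.4.2 gives descriptive statistics by treatment group "where the response ratio approach is utilized". No model or between-arm estimate for the ratio is visible there, although part of that sentence is redacted. SAP 5.4 bases all secondary efficacy analyses on the full analysis set (FAS). SAP Appendix 2 declares no change from the protocol-planned analyses.

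**The concern.** The SAP leaves the planned analyses because they break down at B=0, but the substitute also breaks down there. Eligibility counts three seizure types together (protocol 5.1, criterion 7), so a participant can qualify with no tonic-clonic seizures at all. If such a participant stays free of them, the ratio has no value. If one occurs, the ratio is +1. Among B=0 participants, having a value at all therefore depends on a post-randomisation outcome.

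The switch has two further faults. It depends on double-blind data and has no threshold, so which analysis is run can be settled after the data are seen. It also removes both named analyses for participants with B>0, although that subgroup is fixed before treatment and percent reduction is defined in it.

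What is at stake is the readability of the tonic-clonic results by arm, not the primary result.

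**Working it through.** **Inputs.** The ratio and its range come from SAP 5.4.4.1. Baseline is 8 weeks (56 days) and double-blind treatment is up to 12 weeks (84 days), from SAP 1.2. Cohort 1 has 60 participants randomised 2:1 and later cohorts have 50 randomised 4:1, also from SAP 1.2. Tonic-clonic rates and the share of participants with B=0 are not in the documents and are assumed below.

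**1. Stated range.** Evaluating (T-B)/(T+B) for T and B from 0 to 100 in steps of 0.5, leaving out T=B=0, gives a minimum of -1 and a maximum of +1. The SAP's range is reproduced wherever the ratio exists.

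**2. Values at and near B=0.**
- T=0, B=0: 0/0, undefined. Percent reduction is undefined too.
- One seizure in 84 days, B=0: T = 1 x 28/84 = 0.33; ratio = 0.33/0.33 = +1.
- Thirty seizures in 84 days, B=0: T = 30 x 28/84 = 10; ratio = 10/10 = +1.
- T=20, B=1: ratio = 19/21 = 0.905. A 20-fold rise thus scores better than one new-onset seizure.

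**3. How often the switch might fire.** Assume an unchanged Poisson rate of L per 28 days and full follow-up. Then P(B=0, T>0) = exp(-2L) x [1 - exp(-3L)]. Assume also six such participants.

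| L | P(B=0, T>0) | at least 1 of 6 | at least 3 of 6 |
|---|---|---|---|
| 0.1 | 0.819 x 0.259 = 0.212 | 76% | 11% |
| 0.25 | 0.607 x 0.528 = 0.320 | 90% | 29% |
| 0.5 | 0.368 x 0.777 = 0.286 | 87% | 23% |

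A wider assumption is that 40% to 80% of a cohort have B=0 and 1% to 10% of those have a new-onset case. At least one case then has probability 0.21 to 0.99 (N=60) or 0.18 to 0.99 (N=50). At least three has probability 0.002 to 0.87 (N=60) or 0.001 to 0.78 (N=50). The answer turns on the missing threshold and the unknown rates.

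**4. Effect of leaving out 0/0.** Assume 40 on drug and 20 on placebo, 60% with B=0 (24 and 12), and a mean ratio of -0.1 in both arms among those with B>0 (16 and 8).

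- *Four new-onset cases per arm.* 0/0 dropped: placebo (-0.8+4)/12 = 0.27, drug (-1.6+4)/20 = 0.12, difference 0.15. 0/0 scored 0: placebo 3.2/20 = 0.16, drug 2.4/40 = 0.06, difference 0.10. Dropping widens the gap.
- *Eight per arm.* Dropped: placebo (-0.8+8)/16 = 0.45, drug (-1.6+8)/24 = 0.27, difference 0.18. Scored 0: placebo 7.2/20 = 0.36, drug 6.4/40 = 0.16, difference 0.20. Dropping narrows it.
- *Same proportion in both arms (4 of 12, 8 of 24).* Dropped: 3.2/12 = 0.27 and 6.4/24 = 0.27. Scored 0: 3.2/20 = 0.16 and 6.4/40 = 0.16. There is no difference either way.

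**5. Fractional baseline.** One seizure in 56 days gives B = 1 x 28/56 = 0.5. SAP 5.3.1 requires the cumulative count to equal B, and a whole-number count never equals 0.5. The time-to-event rule therefore needs wording for this even when B>0.

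**The case against.** The strongest reply is that the SAP saw the problem, accepted that the planned analyses would lose sample, and chose a bounded summary instead. Percent reduction is already undefined at B=0, so the ratio did not create the gap. A common score of +1 for new-onset cases follows from any scale capped at 1. All of this is correct, but the ratio still does not close the gap for which it was brought in.

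Four stronger readings are tempting and are not supported:

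- *A single new-onset case triggers the switch.* The SAP speaks of a number of participants and sets no threshold. The fault is that the trigger is open, and the at-least-one probabilities above should not be read as the chance of a switch.
- *A promised treatment comparison is lost.* Protocol 9.2.2 describes secondary efficacy analysis as exploratory, with descriptive statistics by arm and graphs. What is lost is the two named analyses, not a confirmatory test. The SAP also says the ratio will be analysed.
- *The SAP drops 0/0 participants.* It is silent. Dropping is what happens if nobody assigns a value.
- *The arm means show selection rather than effect.* In both unequal examples above the drug arm is better under either handling. Size is distorted there, not the ordering, and scoring 0/0 as 0 is itself a convention.

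The early exit option from Week 4 also shortens some double-blind periods, which lowers the chances in step 3.

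**Conclusion.** The concern holds in limited form. From the text alone, three things are certain: the trigger is unquantified and rests on double-blind data; the switch removes both named analyses for the whole FAS; and the ratio is undefined at T=B=0 and always +1 at B=0, T>0. Without a value for 0/0, B=0 participants are selected on outcome.

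The size is not fixed by the documents. Under the assumed examples, handling of 0/0 moves the arm difference from 0.10 to 0.15 in one case and from 0.20 to 0.18 in the other, so no general direction of bias can be claimed. This is a conditional, exploratory secondary analysis outside the primary test. It should be corrected, but it does not threaten the trial's main conclusion.

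**What to change.** In SAP 5.4.4:

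1. Delete the data-dependent switch. The condition on having enough events can stay.
2. Run time to baseline count and percent reduction in FAS participants with B>0. For the former, define the event as the cumulative count reaching or exceeding B.
3. Among FAS participants with B=0, report by arm the number and proportion with any focal to bilateral tonic-clonic seizure in the double-blind period. SAP 5.5.2.2 already plans a similar count for new cases in follow-up.
4. If the ratio is kept as a supplementary summary, set it to 0 when T=B=0 so that all FAS participants are included, and list it in Appendix 2 as an addition to the protocol-planned analyses. Zero means no change; it keeps these participants in the denominator but does not score them as improved.

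The cost is SAP wording and one extra table. The downside is a smaller sample for the B>0 analyses, which remain exploratory.

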5.4.4.2. Analysis Methods

For each cohort, the time to baseline seizure count will be analyzed for focal to bilateral tonicclonic seizures in the same way as described in Section 5.3.3 for the primary efficacy endpoint. Kaplan-Meier analyses will be presented for the time to reaching baseline monthly seizure count (with 95% CI) for each group (JNJ-813 or Placebo) pooled over CCI , and also treatment group by for all focal to bilateral tonic-clonic seizures. Descriptive summaries of the Kaplan-Meier estimates will be presented by treatment group (JNJ-813 or Placebo) pooled over and also treatment group by , which will include the median with 95% CI and quartiles. The hazard ratio and its 95% CI will be estimated using a Cox proportional hazard regression model, including treatment and baseline CCI . Primary endpoint data from participants on placebo in subsequent cohorts will be combined with those from the previous cohort(s) if the Kaplan-Meier curves of the participants treated with placebo are comparable between cohorts. Where placebo groups are comparable, Kaplan-Meier curves for each cohort will be presented together to demonstrate comparability prior to combining the placebo groups.

In addition, the percent reduction in the double-blind monthly seizure count will be analyzed as described in Section 5.4.1.2 for focal to bilateral tonic-clonic seizures by treatment group and stratum.

Descriptive statistics (N, mean, SD, median, 25th percentile and 75th percentile) will be summarized for each cohort by treatment group (JNJ-813 or Placebo) pooled over colors,

and also treatment group by CCI) where the response ratio approach is utilized.

5.5. Exploratory Endpoint(s) Analysis

All exploratory analyses will be based on the full analysis set apart from Section 5.5.3 (i.e. Seizure freedom and responder rate after the first 4 weeks) which will be based on the modified full analysis set and Section 5.5.4 (Efficacy data in the Open-Label Extension) which will be based on the FASOLE analysis set.

5.5.1. CCI

5.5.1.1. Definition

5.5.1.2. Analysis Methods

For each cohort, descriptive statistics for actual values and changes from baseline for the seizure-related point (4 and 12 weeks) of the double-blind treatment period will be provided by treatment group (JNJ-813) pooled over Mean (±SE) plot for total Mean (±SE) plot for total will be provided for each time point by treatment group and Mean (±SE)

5.5.2. CCI

5.5.2.1. Definition

Participants who continue treatment to the end of the double-blind treatment period (Week 12) or have completed the study early i.e. reached their baseline seizure count before Week 12, and who decide not to participate in the open-label phase weeks after the last dose of study medication.

5.5.2.2. Analysis Methods

To evaluate the CCI , descriptive statistics (N, mean, standard deviation, median, minimum, and maximum) for actual values for the weekly seizure count during each study period (baseline, double-blind and follow-up) will be provided by treatment group (JNJ-813) pooled over CCI , and also treatment group by CCI

for all observable focal-onset seizures. Mean (\pm SE) plot for the weekly seizure count will be provided for each week by treatment group and by stratum.

Furthermore, the following additional safety findings will be reported:

- for each cohort the number and percentage of participants with cluster seizures will be summarized by treatment group (JNJ-813) pooled over treatment group by GCI within each study period (baseline, double-blind and follow-up).
- for each cohort the number and percentage of participants in the follow-up period with focal to bilateral tonic-clonic seizures who had none reported in the baseline or double-blind period will be summarized by treatment group (JNJ-813) pooled over and also treatment group by
- for each cohort the number and percentage of participants in the follow-up period with a seizure rate that is more than twice that of the baseline monthly seizure count will be summarized by treatment group (JNJ-813) pooled over treatment group by The follow-up monthly seizure count is defined as the total number of observable focal onset seizures occurring during the follow-up period, multiplied by 28/X_{FU}, where X_{FU} is the number of days comprising the follow-up period.

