#### Footnotes:

- a) If a participant discontinues treatment before the end of the double-blind treatment period, early withdrawal (EW) visit should be completed
- b)  $\pm 2$  days
- c) When required for practical reasons, the baseline period may be up to 1 week longer or shorter than 8 weeks. Baseline monthly seizure count will be defined as the number of observable focal onset seizures recorded during the baseline period, multiplied by 28/XBL, where XBL is the number of days comprising the baseline.
- d) Participant should come to the study visit in fasted conditions (at least 4 hours) when possible
- e) Visit in the morning hours before noon.
- f) Participants will be contacted by phone during the baseline period to confirm correct use of the e-diary. This contact should take place at least 4 weeks after the start of the baseline period, but multiple contacts are allowed when required.
- g) After completion of all visit assessments (except post-dose PK blood sample).
- h) Except in-clinic doses during visits
- i) To be collected before dosing and when possible in fasting condition
- j) During Visit 2, also collect a blood sample for biomarkers at 2 hours post dose (together with PK-sample)
- k) Collect with clinical laboratory sample.
- l) Detailed timepoints for PK sample collection are provided in Table 4: PK sampling Strategy
- m) Only levetiracetam or brivaracetam and JNJ-40411813, at EW only when EW visit is after Visit 6.
- n) CCI
- o) Only seizure counts. Only subjects who continued treatment to the end of the double-blind treatment period (Week 12) or have completed the study as per Section 7.2
- p) CCI
- q) Systolic and diastolic blood pressure, heart rate and body temperature (oral or tympanic)
- r) Triplicate ECG at screening. Single ECG at the other timepoints.
- s) In women of childbearing potential only. Serum pregnancy test at screening and a urine pregnancy test at the other visits.

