# **Duration of study periods**

Participants will be dosed with study intervention over 12 weeks. This is a common duration of evaluation of AED's in clinical studies (EMA 2018, FDA 1981). After at least 55 participants in a cohort 1 and at least 45 patients in Cohort 2 have completed 4 weeks of treatment, an interim

unblinded review of all cumulative safety, PK and efficacy data of JNJ-40411813 available to that date will be performed to decide on the dose in the following cohort. If the results of the review are inconclusive, a second interim review of the same cohort may be done after the last participant has completed the 12-week visit.

Based on an evaluation of the variability of seizure count in prior epilepsy studies completed by the sponsor (Janssen, data on file), a baseline duration of 8 weeks was considered to give a more accurate and representative estimate of monthly seizure count than shorter periods.

The double-blind study period will be followed by a follow-up period of 2 weeks if the participant does not take part in the OLE period. The dose will not be tapered after completion of the double-blind study period. Although there are no signals of a rebound effect after stopping the treatment with JNJ-40411813 from preclinical studies or previous clinical studies, the change of seizure count after stopping the treatment will be investigated in the follow-up period.

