4. POPULATIONS (ANALYSIS SETS) FOR ANALYSIS

For purposes of analysis, participants will be classified into the following analysis sets. For each analysis set described below, participants will be analyzed according to the planned study intervention irrespective of what they actually received.

Analysis Sets	Description				
Enrolled	All participants who sign the ICF.				
Randomized The randomized analysis set includes all participants who were randomized in					
Full Analysis Set	The full analysis set (FAS) includes all randomized participants assigned to receive				
(FAS)	study intervention and have both baseline and postbaseline seizure data. This definition				
	is the same as the ITT set.				
Full Analysis Set:	The FASOLE analysis set includes all FAS participants who received at least 1 dose of				
Open-Label	study intervention in the OLE phase.				
Extension					
(FASOLE)					
Compliance	The compliance analysis set (CAS) includes a subset of participants in the FAS who				
Analysis Set	were in compliance with their medication intake. In other words, exclude those who with				
(CAS)	<80% compliance for medication intake. Medication intake data will come from the dru				
	accountability data collected at monthly visits.				
"Modified" FAS	The modified FAS includes a subset of participants in the FAS who remained in the				
	treatment period beyond 4 weeks. In other words, participants who exit the study by 4				
	weeks having reached their pre-randomization baseline seizure count will not be				
	included.				
Safety (SAF)	The safety analysis set includes all randomized participants who received at least 1 dose				
C-f-t O	of JNJ-40411813 or placebo in the double-blind phase.				
Safety: Open-	The SAFOLE analysis set includes all randomized participants who received at least 1				
Label Extension dose of study intervention in the OLE phase. This analysis set is the same as the					
(SAFOLE)	FASOLE analysis set.				
PK Analysis Set	The PK analysis set (PKAS) included all randomized participants who have received at				
(PKAS)	least 1 dose of JNJ-40411813 and have at least 1 valid blood sample drawn for PK				
	analysis.				

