Participants who continued treatment to the end of the double-blind period (Week 12) or have completed the study (as defined above) and have not elected to participate in the OLE will go into the follow-up phase. In the follow-up phase, participants will continue to record only the number of seizures using the e-diary until 2 weeks after the last dose and will have a telephone follow-up visit at 2 weeks ± 2 days after the last dose. The analysis reference start date of the follow-up analysis phase is the day after the reference end date for the double-blind phase. The analysis reference end date of the follow-up analysis phase is the maximum of the telephone follow-up visit date or the e-diary follow-up date.

Open-Label Extension Phase

For participants electing to participate in the OLE, the reference start date of the OLE phase will be either the date of last study drug intake by the participant in the double-blind period for subjects who continue into the OLE without an interruption of ≤4 weeks from the double-blind period, or the date of the OLE baseline visit when there is an interruption of >4 weeks (i.e. the last visit of the double-blind period was more than 4 weeks ago). Participants participating in the OLE without an interruption of ≤4 weeks from the double-blind period will not have the follow-up visit (Visit 8), and those with an interruption of >4 weeks will complete the follow-up visit. The analysis reference start date for the OLE phase is the date of the last dose taken in the double-blind phase. The analysis reference end date of the OLE phase is either the date when the last dose of study drug is taken in the OLE phase (Visit OLE11), the date OLE is stopped by the sponsor or the date of early withdrawal from the OLE phase. The open-label efficacy data will be summarized by the double-blind treatment group in the form of an intervention sequence (PBO/JNJ and JNJ/JNJ).

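### SAP 5.5.2.2 describes seizures after stopping mainly through unpaired weekly counts, so who contributes follow-up data can create or hide a change

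*SAP*

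**What the plan says.** Protocol 4.2 (Duration of study periods) notes that the dose is not tapered and that "the change of seizure count after stopping the treatment will be investigated in the follow-up period".

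SAP 5.5.2.2 implements this with "descriptive statistics (N, mean, standard deviation, median, minimum, and maximum) for actual values for the weekly seizure count during each study period", for baseline, double-blind and follow-up, and a mean (±SE) "plot for the weekly seizure count will be provided for each week by treatment group and by stratum". The visible text names no change score and no fixed set of participants. By contrast, SAP 5.5.1.2 plans changes from baseline for another exploratory endpoint.

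The analysis set comes from SAP 5.5: "All exploratory analyses will be based on the full analysis set apart from Section 5.5.3" and Section 5.5.4. SAP 4 admits to that set randomised participants assigned to "study intervention and have both baseline and postbaseline seizure data", so follow-up data are not required.

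Fewer people supply follow-up counts. Footnote o of the Protocol 1.2 schedule limits them: "Only subjects who continued treatment to the end of the double-blind treatment period (Week 12) or have completed the study as per Section 7.2". SAP 5.1 adds that those who "have not elected to participate in the OLE will go into the follow-up phase". Protocol 7.2 counts as completers those who leave after reaching or exceeding their baseline count. Protocol 10.5.1 makes OLE entry depend on the investigator expecting benefit.

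SAP 5.5.2.2 also lists two within-participant follow-up measures: a rate above twice the participant's own baseline, and focal to bilateral tonic-clonic seizures in someone who had none before follow-up.

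**The concern.** A change after stopping is a question about the same people measured twice. The planned table and plot set side by side averages taken over different people. Baseline and the first double-blind weeks hold nearly everyone. Later double-blind weeks lose participants who exceeded their baseline count and chose to leave. Follow-up then contains such leavers and Week 12 completers, less those who went on to the OLE. High-count participants can thus be absent from the late double-blind weeks and return in follow-up.

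Two errors are possible. A step up may be shown when nobody's rate changed, or a real rise may be lost in a shift of case mix, given an entry range of 3 to 100 seizures per 28 days. Either could mislead later decisions about how seizures behave after an untapered stop.

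**Working it through.** The plan states no figure for this analysis, so there is none to reproduce.

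**1. Arithmetic illustration (assumed numbers).** Take 20 participants at 2 and 20 at 8 seizures per week. All fall to 0.75 × baseline on treatment and stay there after stopping.

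- Baseline mean = (20×2 + 20×8)/40 = 5.00. Double-blind mean = 0.75 × 5.00 = 3.75.
- Follow-up mean = 0.75 × (L×2 + H×8)/(L + H), where L and H are the low- and high-rate participants followed.

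| Followed (L, H) | Follow-up mean | Against 3.75 | True change |
|---|---|---|---|
| 4, 10 | 0.75 × 88/14 = 4.71 | +26% | 0% |
| 10, 4 | 0.75 × 52/14 = 2.79 | −26% | 0% |
| 6, 6 | 0.75 × 60/12 = 3.75 | 0% | 0% |

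A rebound can also be hidden. If every followed participant rises to 1.5 × own baseline and L = 10, H = 2, the follow-up mean is 1.5 × 36/12 = 4.5. That is below the baseline mean of 5.00 and only 20% above the double-blind mean, although each person's rate has doubled (1.5/0.75).

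**2. Simulation without early exit.** Inputs: 40 active participants; weekly baseline rate log-normal, median 2.5, log SD 0.8, limited to 0.75–25; Poisson counts; median on-treatment rate 0.85 × 0.7 = 0.595 × baseline; 8, 12 and 2 weeks per period; no change after stopping. Entry to follow-up is assumed. Follow-up minus double-blind, seizures per week:

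| Who enters follow-up | Unpaired means | Same participants |
|---|---|---|
| Responders 10%, worsened 60%, others 30% | +0.59 | −0.07 |
| Responders 60%, worsened 10%, others 30% | −0.47 | +0.04 |
| 30% of all | +0.01 | 0.00 |

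**3. Simulation with early exit, no change after stopping.** From the plan: cohorts of 40 JNJ or 20 placebo, 3–100 seizures in each baseline half, placebo reduction 15%, further reduction 50% or 30% on JNJ. Assumed:

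- median 10 seizures per 28 days, log SD about 0.6–0.8
- daily count variance twice the mean; log SD of individual response 0.5
- weekly exit checks from Day 28, with 50–80% of those eligible leaving at each
- OLE uptake either unrelated to outcome (50–70%) or higher in responding completers

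| Comparison | Median ratio | Cohorts with a false rise above 50% |
|---|---|---|
| Follow-up / double-blind mean (table) | about 0.92–1.12 | about 2–16% |
| Follow-up / observed weeks 9–12 (plot) | about 1.06–1.56 | – |
| Same participants, follow-up / own double-blind | about 0.88–0.99 | 0–4% |

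The double-blind mean here averages one rate per participant. The SAP does not say whether the table does that or pools person-weeks. With pooling, the median ratio was 1.05–1.12 with equal OLE uptake and 1.23–1.24 with selective uptake. Exit uptake drives the weeks 9–12 contrast: at 10% leaving per check, with equal OLE uptake and the 50% effect, its median ratio is 1.00.

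**4. What the yes/no measures leave out.** A participant at 0.4 × baseline on drug who reaches 1.5 × baseline after stopping has risen 1.5/0.4 = 3.75-fold, yet stays under the twice-baseline threshold. The tonic-clonic measure records new occurrence of one seizure type. Neither gives the size of the change from the on-treatment level.

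**The case against.** SAP 5.5.2.2 is not purely unpaired. A reader might infer that the effect of stopping is judged from the period means alone. The documents do not support that, because the two yes/no measures compare each participant with their own history and do not move when different people form the baseline mean. Own baseline is also a sensible reference for rebound: if a drug halves seizures, a mere return to baseline doubles the rate from the on-treatment level. So the baseline contrast in the plan is not a flaw. What is missing is the other contrast and any measure of size.

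A reader might also infer a large upward artefact. That is not established. The biggest ratios concern weeks 9–12, which can only be read off the plot, and they shrink or vanish when few eligible participants leave; Protocol 4.1 lets them continue double-blind treatment. Section 2 of the working shows that the sign can reverse. Nor is a spurious drug-specific rebound shown, because placebo has more early exit (54% against 21% on JNJ in one run with the 50% effect) and so can show the larger artefact.

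The per-period N and median make the drop in numbers visible, though they do not correct it. Participants with a gap of more than 4 weeks before the OLE do complete follow-up (Protocol 10.8.2.1), which dilutes selection by OLE choice to an unknown degree.

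Part of SAP 5.5.2.1 is blacked out. A restriction to one common set there would remove the point. The surviving words say only who gives follow-up data, and SAP 5.5 names the full analysis set.

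**Conclusion.** The point holds for the main table and the weekly plot: as the visible text stands, they can show or hide a change after stopping that comes only from who contributes. In the tabulated contrast the distortion under no true change is modest at the median, roughly −8% to +12%. A false rise above 50% still occurs in about 2–16% of cohorts, against 0–4% with paired data. From the plot, the false rise against weeks 9–12 is about 6–56% at the median when half or more of those eligible leave at each check, and it can be nil when few do.

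These sizes rest on assumed exit uptake, OLE uptake and seizure-rate distribution, none of which the documents give. The direction is not fixed. If follow-up entry were unrelated to seizure rate or response, the tabulated contrast would be nearly undistorted, but early exit could still distort the plot. The analysis is exploratory and descriptive, and it does not touch the primary result.

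**What to change.** In SAP 5.5.2.2:

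- For participants with follow-up seizure data, compute each one's 28-day rate in baseline, double-blind and follow-up.
- Summarise the within-participant change from double-blind to follow-up and from baseline to follow-up descriptively, JNJ and placebo side by side.
- Draw the three-period weekly plot in this same fixed set, and flag early exiters and Week 12 completers.
- Keep the existing bullets.

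The cost is SAP wording, one table and one figure, with no new data. There are two limits. The set is small: in most of the simulated scenarios, about 10–16 of 40 JNJ and 7–8 of 20 placebo participants, and 3–4 where placebo has 10. Formal between-arm intervals or separate exiter and completer analyses would therefore carry little information. The paired ratio also runs slightly below 1 with no true change (about 0.88–0.99), mainly because exiters leave on a high run, so it should be read against placebo.
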